The key secondary hypothesis is that the MQS predicts ADD better than the SICU optimal mobilization score [SOMS] (Schaller et al., 2016).

We also hypothesize that the MQS predicts ICU length of stay, hospital length of stay, functional independence measure (mmFIM) at ICU and hospital discharge, 3-month mortality, change in muscle mass quantified by change in RF-CSA, ICU coma- and delirium-free days, ICU ventilator-free days, ICU vasopressor-free days, ICU neuromuscular blocking agent free days, opioid dosage, corticosteroid days, and physical work capacity 3 months after hospital discharge quantified by the Duke Activity Status Index (DASI).

Covariate Data

Predefined confounders in multivariable adjusted analyses include APACHE2 (Knaus, Draper, Wagner, & Zimmerman, 1985), sex-adjusted rectus femoris cross sectional area (RFCSA) (Janssen, Heymsfield, Wang, & Ross, 2000) measured via bedside ultrasound upon admission, and the Risk Quantification Index for 30-day Postoperative Morbidity (PSS morbidity) (Dalton et al., 2011).

RFCSA measured by bedside ultrasound has been shown to be an independent predictor of adverse patient outcomes (Mueller, Eikermann 2016).

RFCSA will be adjusted for sex using published skeletal muscle mass values of the lower body of healthy adults (Janssen et al., 2000). Thus, RFCSA of female patients are multiplied with the coefficient 1.484, whereas male patients represent the reference group (adjustment coefficient 1). Sex-adjusted RFCSA will be used for further statistical analyses.

Statistical Analysis

All analyses are performed prospectively with prespecified endpoints and statistical methods.

Primary analysis

Unadjusted Analysis: We will conduct univariate logistic regression analysis to investigate the association between mobilization dose quantified by MQS and ADD.

Adjusted analysis: Multivariable logistic regression (mean daily mobilization dose (MQS)/ ADD) analyzing whether mobilization dose predicts adverse discharge independent from the defined covariates (APACHE2, PSS Morbidity score, and sex adjusted admission RFCSA).

Secondary analyses

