We will perform Net Reclassification Index and c-statistics to compare the predictive capability for ADD of the MQS to the SOMS. To further confirm the robustness of our results we will conduct Aikaike Information Criterion (AIC) and likelihood ratio test. AIC provides the relative quality of the estimated model. The likelihood ratio test compares the goodness of fit of two statistical models.

Multivariable logistic regression will be performed to evaluate the relationship between mean daily mobilization dose and other binary secondary outcomes controlling for above defined covariates. Zero truncated negative binomial regression will be used to analyze the association between mobilization dose and the secondary outcomes ICU and hospital length of stay. Negative binomial regression will be used to analyze the association between mobilization and the secondary outcomes coma- and delirium-free days, NMBA-free days, ventilator-free days, and functional independence measure (mmFIM) at ICU and Hospital discharge.

We will use linear regression to analyze the association between mobilization and physical work capacity 3 months after hospital discharge quantified by the Duke Activity Status Index (DASI) and opioids dosage (mg), if normality assumption is satisfied. Otherwise, transformation of the variables will be performed, and the transformed variables will be used as the outcome in the linear model.

Planned Sensitivity Analyses

Evaluation of confounder model: AUC-Analysis including the predefined confounders to determine the Area Under the receiver operator curve.

Categorized exposure variable: (2-quantile [high, low mobilization dose], tertiles [low, intermediate, high mobilization dose])

Alternative Exposure Variable: For each patient, mobilization data will be centered, and we will perform simple linear regression with the individual mean mobilization dose being the estimated intercept of each patient. The estimated slope from the linear regression will be considered as the change rate of mobilization dose. Two exposures will be included in our model, the slope of the mobilization dose and the intercept. We will conduct multivariable logistic analysis controlling for the same confounder variables (expected 4DoF: Intercept, Slope, APACHE2, RFCSA (continuous), PSS morbidity) from the primary analysis.

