Primary hypothesis

The primary hypothesis is that RFCSA is an independent predictor of mobilization dose in the SICU.

Statistical Analysis

All analyses are performed prospectively with prespecified endpoints and statistical methods.

We will conduct a generalized linear mixed effect model to analyze whether the RFCSA quantified via bedside ultrasound is an independent predictor of daily mobilization dose in the ICU.

Predefined confounders include the Barthel Index at hospital admission, APACHE2 and Charlson Comorbidity Index (CCI).

Secondary analysis

We will conduct a generalized linear mixed effect model to analyze whether the RFCSA quantified via bedside ultrasound is an independent predictor of daily mobilization dose in the ICU utilizing an alternative exposure variable. The exposure variable will be the binary variable "Sarcopenia

yes/no". Sarcopenia is quantified by RFCSA assessed through bedside ultrasound measurements within 48h. We will apply Youden's Index to define the optimal cutoff point of RFCSA for Sarcopenia. (Mueller, Eikermann 2016).

Sarcopenia is a clinical syndrome that describes progressive and generalized loss of skeletal muscle mass and strength and is associated with patient outcomes. (Delmonico, Harris, Lee, J Am Geriatr Soc, 2007)

Sample Size and Power

Based on data obtained by the same centers in the SOMS trial (Schaller et al., 2016) there is a correlation between mobilization dose and discharge disposition of 0.25. We therefore calculate that a sample size of 150 patients provides a power of >0.8 to identify a significant effect (alpha-error: 0.05) for our primary outcome.

Data collection

Data collection

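### The key secondary comparison (MQS versus SOMS) rests on an NRI with no stated form, inference method or deciding role; computed category-free with its usual z-test, it would declare false winners at about five times the nominal rate

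*SAP*

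**What the plan says.** SAP section 2, under Secondary Hypothesis, ranks the claim: "The key secondary hypothesis is that the MQS predicts ADD better than the SICU optimal mobilization score". Under Statistical Analysis, Secondary analyses, the method is: "We will perform Net Reclassification Index and c-statistics to compare the predictive capability for ADD of the MQS to the SOMS". The next sentence adds supporting measures: "To further confirm the robustness of our results we will conduct Aikaike Information Criterion (AIC) and likelihood ratio test".

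The SAP does not state:

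- the form of the NRI (category-free or categorical) or any risk cut-offs;
- how a standard error, interval or p-value will be obtained, or whether the models are refitted or validated internally;
- whether the two models being compared include the covariates;
- which measure settles the hypothesis if NRI and c-statistic disagree.

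Under Planned Sensitivity Analyses, the NRI is used again, with the Brier score and c-statistics, to compare the primary model with the intercept-and-slope model. It is equally unspecified there.

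**The concern.** MQS and SOMS are rival scores, so the two models are not nested. Both are fitted and compared in the same patients. The category-free NRI uses only the sign of each patient's change in fitted risk. A chance difference between the two fitted coefficients therefore moves many patients in the apparently right direction together. The usual variance treats the fitted risks as known and patients as moving independently, so it is too small.

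At stake is the claim that the new score beats the established one. With two measures listed and no deciding rule, that claim could be made on the less reliable of the two. The primary analysis, a logistic regression of ADD on MQS, is not affected.

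**Working it through.** **Inputs from the SAP.** N = 150 ("a sample size of 150 patients provides a power of >0.8 to identify a significant effect"). Effect size: "there is a correlation between mobilization dose and discharge disposition of 0.25". Alpha is 0.05, given for the primary outcome only and without sidedness; two-sided is assumed here. Covariates are three: APACHE2, PSS morbidity and sex-adjusted RFCSA.

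**Assumptions not in the SAP.** ADD rate 30-50%; correlation between the scores 0.3-0.9; normally distributed scores; example risk cut-offs.

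**Step 1: the SAP's own figure.** Fisher's z gives power = Φ(atanh(0.25) × √147 − 1.96) = Φ(0.2554 × 12.124 − 1.96) = Φ(1.137) = 0.872. The stated power above 0.8 is reproduced, for the primary outcome. The MQS-SOMS comparison has no power statement.

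**Step 2: the usual category-free test.** NRI = [P(up | ADD) − P(down | ADD)] + [P(down | no ADD) − P(up | no ADD)]. When every patient moves up or down, the usual null SE is √(1/n₁ + 1/n₀), with n₁ patients with ADD and n₀ without.

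- ADD 30%: √(1/45 + 1/105) = 0.178. If this SE were right, the median |NRI| under equality would be 0.6745 × 0.178 = 0.120.
- ADD 50%: √(1/75 + 1/75) = 0.163. The corresponding median is 0.6745 × 0.163 = 0.110.

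The simulated median |NRI| with no true difference is about 0.19 or more. The true spread is therefore about 0.19/0.120 = 1.58 to 0.19/0.110 = 1.73 times the SE used. The implied two-sided rejection rate is 2 × [1 − Φ(1.96/1.58)] ≈ 22% to 2 × [1 − Φ(1.96/1.73)] ≈ 26%, in line with the direct simulation below.

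**Step 3: simulation under equality.** Both scores were given the same predictive strength (in most runs a correlation of 0.25 with ADD), and one logistic model was fitted per score, with and without three covariates. Most scenarios used 1,500-2,000 trials. At a rate of 25% and 2,000 trials the Monte Carlo SE is √(0.25 × 0.75/2000) = 1.0 percentage point.

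| Method | Declares a winner (nominal 5%) |
|---|---|
| Category-free NRI, usual z-test | about 22-28%; MQS wins in about 11-15% (nominal 2.5%) |
| Category-free NRI, bootstrap with fitted models held fixed | about 25% |
| Four-category NRI (0.2/0.4/0.6), z-test | 8.5-26% |
| Three-category NRI (0.2/0.5), z-test | about 9-14% |
| One cut, at 0.5 or at the event rate, z-test | near 5% (4.0-6.8% at the event rate) |
| Category-free NRI, bootstrap refitting both models | about 3-6% |
| c-statistic difference, DeLong | about 1-5% |
| c-statistic difference, bootstrap refitting both models | about 3% |

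The NRI refitting-bootstrap row rests on few trials (300 for the 3-6% range; Monte Carlo SE at 5% = √(0.05 × 0.95/300) = 1.3 points).

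**Step 4: sensitivity.** The category-free z-test rejects in 17% when the correlation with ADD is 0.15 and in 30-31% when it is 0.35. At N = 1000 it still rejects in 28-31%, so a larger sample does not cure it. A coarser SOMS scale gives 25%. The mean z is near 0 throughout.

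**Step 5: disagreement between the two named measures.** Under equality, the category-free NRI favoured MQS while DeLong did not in about 10-13% of trials.

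**Step 6: power of a valid comparison.** In a scenario where SOMS adds nothing beyond MQS (score correlation 0.7, N = 150), MQS superiority was detected in about 12% of runs by DeLong and 16% by the refitting bootstrap. A further run gave 15-18%.

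**The case against.** The strongest reply is that the failing procedure is not written in the SAP. It names no category-free form, no z-test and no NRI threshold, and the c-statistic stands in the same sentence. This largely stands. A reader might infer that the SAP commits to an invalid test, or that the NRI decides because it is listed first. The text supports neither. If both measures had to favour MQS, the false-positive rate for MQS would be only about 0.8-1.7%. What remains is that, without cut-offs, the category-free index is the only one computable from the text, that nothing excludes its standard test, and that nothing says both measures must agree.

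A second stronger inference is that the NRI favours MQS. It does not: false winners fall on either side about equally. Only the false wins for MQS, 11-15%, bear on the stated hypothesis.

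A third is that every NRI is unsound here. A single cut, or a bootstrap that refits both models, stays near nominal.

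It is also fair that the SAP sets no significance level for this hypothesis. The comparison with 5% and 2.5% assumes a two-sided 0.05 test. A one-sided 5% test would use the lower critical value 1.645 and could only raise the false-win rate for MQS above 11-15%.

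**Conclusion.** The point holds in conditional form. The SAP assigns its key secondary hypothesis to the NRI and c-statistics without fixing the NRI's form, its inference or which measure decides. The most direct reading of the NRI, category-free with its usual z-test, gives a false winner in about 22-28% of trials and a false win for MQS in about 11-15%. Multi-category versions were also inflated, generally by less. Other versions would have been acceptable.

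The figures rest on assumed ADD rates of 30-50%, assumed score correlations and normally distributed scores. The inflation appeared in every category-free z-test scenario run. This goes beyond missing detail, because the unstated choice determines whether the error rate is near nominal or several times it. It concerns a secondary hypothesis and should be corrected before the comparison is run.

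**What to change.** In section 2, Secondary analyses, state that:

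- the key secondary hypothesis is decided by the difference in c-statistic between the model with MQS plus the three covariates and the model with SOMS plus the same covariates;
- its 95% CI comes from a paired patient-level bootstrap that refits both models in each resample;
- the NRI is supportive only, reported as separate event and non-event parts, with any interval from the same refitting bootstrap and never the standard z-test;
- AIC and the likelihood ratio test do not decide the hypothesis.

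Apply the same rule for the NRI to the intercept-and-slope comparison under Planned Sensitivity Analyses. That comparison was not simulated here.

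**Cost.** A few sentences and a short bootstrap; no new data. The real price is power: with 150 patients a valid comparison detects a true MQS advantage in only about 12-18% of runs in the scenario of step 6. The SAP should say so, and should say that failure to show superiority is not evidence that the two scores are equivalent.

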Statistical Analysis Plan

Effects of mobilization dose in surgical intensive care unit patients on adverse discharge disposition

Original Date: August, 20, 2018

Table of Contents

1. Primary and Secondary Aim Overview.....	2
2. Primary aim.....	2
Hypotheses.....	2
Covariate Data.....	3
Statistical analysis.....	3
3. Secondary aim.....	5
Hypothesis.....	5
Statistical Analysis.....	5
4. Sample Size.....	6
5. Data collection.....	6

1. Primary and Secondary Aim Overview

Primary Aim

The primary aim of this study is to assess the effects of mobilization dose in critically ill patients on adverse discharge disposition (ADD) (primary outcome). The primary hypothesis of this study is that the mobilization dose in the surgical intensive care unit measured by Mobilization Quantification Score (MQS) is associated with ADD.

Secondary Aim

The secondary aim is to evaluate the association between rectus femoris cross sectional area (RFCSA) measured by bedside ultrasound within 48 hours of enrollment and mobilization dose received in the surgical intensive care unit (SICU).

2. Primary Aim

This study aim is driven by the research hypothesis that the MQS - a new method to quantify mobilization dose based on intensity and duration with more granularity than currently used mobilization quantification instruments - reflects the improving effects of early mobilization on discharge disposition.

Exposure variable

The primary exposure variable is the mean daily mobilization dose quantified by the MQS. The MQS is a newly developed score that quantifies mobilization provided by SICU nurses and physical therapists incorporating the mobilization level as well as its duration. The MQS is calculated daily throughout the SICU stay and will be divided by the number of ICU days to arrive at the exposure variable mean daily mobilization dose.

The secondary exposure variable used for comparison is the SICU optimal mobilization score (SOMS).

Primary Outcome

The primary outcome ADD is defined as discharge to facilities providing long-term care assistance for daily activities, including nursing homes and skilled nursing facilities, hospice at the patient's home, hospice in a healthcare facility, or in-hospital mortality.

Hypotheses

Primary Hypothesis

The primary hypothesis is that mobilization dose quantified via MQS predicts adverse discharge disposition.

Secondary Hypothesis

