Date intubated, Date extubated, Reintubation (y/n)

ICU Discharge

mmFIM score in domains transfer and locomotion, ICU Discharge [date], ICU LOS, number of PT visits, ICU Readmission, weight at ICU discharge, medical interventions during ICU stay

Hospital Discharge

Hospital Discharge [date], Hospital Readmission, Hospital LOS, In-Hospital Mortality, Discharge destination, Total costs of care

Phone Call

DASI, Readmission to any Hospital, One-month mortality, Three-month mortality.

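### The length-of-stay models do not separate death from live discharge, so their coefficients mix leaving alive sooner with dying sooner

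*SAP*

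**What the plan says.** Both lengths of stay are named among the outcomes in section 2, Secondary Hypothesis: "We also hypothesize that the MQS predicts ICU length of stay, hospital length of stay". The same sentence lists 3-month mortality. Section 2, Secondary analyses, fixes the model: "Zero truncated negative binomial regression will be used to analyze the association between mobilization dose and the secondary outcomes ICU" and hospital stay.

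The SAP does not say how a patient who dies before discharge enters this model. It gives no survivor restriction, censoring, competing event or worst-value rule, and none of the planned sensitivity, subgroup or exploratory analyses takes up the point.

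Deaths are expected. The primary outcome (section 2, Primary Outcome) ends with "hospice at the patient's home, hospice in a healthcare facility, or in-hospital mortality", and the primary hypothesis is that MQS predicts that outcome. The exposure is a whole-stay average (section 2, Exposure variable): "The MQS is calculated daily throughout the SICU stay and will be divided by the number of ICU days". The Data collection section lists the items needed to tell the two endings apart: "Hospital Discharge [date], Hospital Readmission, Hospital LOS, In-Hospital Mortality, Discharge destination". The ICU discharge date is listed there too.

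**The concern.** A count regression sees only the number of days. Death on day 3 and discharge home on day 3 both enter as 3, although one is the worst result and the other among the best. If the exposure were unrelated to death, this would add noise but little distortion. The plan, however, expects the exposure to be related to a death-containing outcome and to later mortality. A coefficient below or above 1 then cannot be read as faster or slower recovery, because differences in who dies and when also move it.

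At stake is the interpretation of two prespecified secondary outcomes. Silence on deaths also leaves their handling open to a choice made after the data are seen.

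**Working it through.** **The plan's own figure.** The only computed figure is the power for the primary outcome (r = 0.25, 150 patients, alpha 0.05). By Fisher z: atanh(0.25) × √147 − 1.96 = 0.2554 × 12.124 − 1.96 = 1.137, and Φ(1.137) = 0.87. The stated power above 0.8 is reproduced. This point does not depend on it.

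**Inputs.** From the SAP: the model, the outcomes and the exposure. The SAP gives no mortality, death times or effect on death, so these are assumptions and are varied below.

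**Step 1: mechanism with competing hazards.** With constant hazards λ (live discharge) and μ (death), mean stay = 1/(λ + μ). Assume λ = 0.10 and μ = 0.018 per day, so mortality is 0.018/0.118 = 15%. Halve μ and leave λ alone: the ratio of mean stays is 0.118/0.109 = 1.08. The stay lengthens although live discharge is untouched.

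**Step 2: the planned model fitted.** 60,000 simulated patients per cell; Weibull live-discharge times (shape 1.3), exponential death times, stay = day of the first event, standardised exposure. The exposure has no effect on live discharge, so the true ratio is 1.00. Fitted ratio of days per SD:

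| Mortality | Death HR 1.0 | HR 0.7 | HR 0.5 |
|---|---|---|---|
| about 5% | 1.00 | 1.02 | 1.03 |
| about 10% | 1.00 | 1.02 | 1.07 |
| about 15% | 1.00 | 1.04 | 1.10 |
| about 20% | 1.00 | 1.06 | 1.14 |

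The first column isolates the cause: without a link between exposure and death there is no distortion. Further fits of this kind, up to about 25% mortality, gave 1.01-1.07 at HR 0.7 and 1.02-1.14 at HR 0.5.

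**Step 3: a real shortening.** Let the true time ratio for live discharge be 0.90 per SD, at about 15% mortality:

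| Fitted ratio | Death HR 1.0 | HR 0.7 | HR 0.5 |
|---|---|---|---|
| all patients | 0.91 | 0.96 | 1.01 |
| survivors only | 0.91 | 0.94 | 0.97 |

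The effect is diluted or lost, and restricting to survivors recovers only part of it.

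**Step 4: the sign depends on when deaths occur.** Suppose the exposure changes only the probability of death p, with stays fixed by outcome. Mean stay = p·m(dead) + (1 − p)·m(alive), so a lower p lengthens the mean only if m(dead) < m(alive). Take p = 0.148 at the mean exposure; an odds ratio of 0.5 gives p = 0.080 one SD higher. With m(alive) = 10 days:

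- m(dead) = 4: (10 − 6 × 0.080)/(10 − 6 × 0.148) = 9.52/9.11 = 1.04
- m(dead) = 10: 1.00
- m(dead) = 18: (10 + 8 × 0.080)/(10 + 8 × 0.148) = 10.64/11.18 = 0.95

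The planned model fitted to such mixtures gave 1.06, 1.00 and 0.94. A second mixture (lognormal stays with log-SD 0.7, median 7 days to discharge, odds ratio 0.5, about 20% mortality) gave 1.05, 1.01, 1.00, 0.98 and 0.94 for median times to death of 4, 6, 7, 9 and 12 days. With an odds ratio of 0.75 and deaths at 4 days it gave only 1.01-1.02.

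**Step 5: consequence at 150 patients, early deaths only.** With 15-22% mortality, an odds ratio for death of 0.5 per SD, and medians of 4 days to death and 7 to discharge (400 runs per scenario), a null effect was declared significantly longer in 15-25% of runs against a nominal 2.5%. A true ratio of 0.88 appeared as 0.94-0.96, and power fell from 58% to 15-23%. This is one corner of the range, not a forecast for this study.

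**The case against.** The strongest case against runs as follows.

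- *The SAP is silent; it does not say that early deaths count as short stays.* This stands as a matter of wording: the statement describes what the named model does by default. But the choice of model is made in this SAP, and a count model without further instruction cannot tell the two endings apart.
- *The direction is not fixed.* This stands in full. A reader might infer that any survival benefit of mobilization must appear as a longer stay. The SAP gives no death times, and step 4 shows that the distortion vanishes when deaths are as late as discharges and reverses when they are later. At about 5% mortality it is small in any case.
- *No hypothesis of fewer deaths is stated.* This is correct. The SAP says that MQS predicts adverse disposition and 3-month mortality, and it speaks of improvement only for discharge disposition. The point needs only an association between exposure and death.
- *Total days occupied, dead or alive, is a legitimate quantity.* It is, as a description of resource use. It does not show whether patients leave alive sooner, and the SAP does not say which is meant.
- *The remedy is imperfect.* This stands: hospice discharge has to be classed, a survivors-only analysis stays biased, and a whole-stay exposure is unknown at time zero in a hazard model too.

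**Conclusion.** The point holds for the ambiguity, not for a fixed direction of bias. As planned, the length-of-stay coefficients cannot separate leaving alive sooner from dying sooner, and the plan itself expects the exposure to be linked to death. With no true effect on live discharge, the fitted ratio per SD is about 1.01-1.14 if deaths are early or live-discharge hazards are unchanged (about 5-25% mortality, death hazard ratio 0.5-0.7), about 1.00 if deaths are as late as discharges, and about 0.94-0.99 if they are later. All of these rest on assumed mortality, timing and effect on death.

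A reader might also infer that the main result is compromised. It is not: the primary logistic analysis of adverse discharge disposition does not use these models. This is a change that should be made to secondary analyses, not one on which the study depends.

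**What to change.** In section 2, Secondary analyses:

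1. Make the main length-of-stay analyses time to ICU discharge alive and time to hospital discharge alive, with death as a competing event. Report cause-specific hazard ratios for live discharge and for death, with the same covariates (APACHE II, PSS morbidity, sex-adjusted RFCSA). Fine-Gray models are optional.
2. State how discharge to hospice is classed, since the primary outcome groups it with death.
3. State that for patients who die the recorded discharge date is the date of death, because the data list shows no separate item for it.
4. Keep the zero-truncated negative binomial model as a descriptive secondary analysis, overall and in survivors, and note that the survivors-only version does not fully remove the bias.

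The cost is SAP wording; discharge dates, in-hospital mortality and destination are already collected. The effect is then reported as a hazard ratio instead of a ratio of days. The change does not cure a separate problem: mean daily MQS is averaged over the ICU stay itself, so exposure and ICU stay remain structurally linked.

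### ICU free-day outcomes go into a negative binomial model with no offset: if counted within the ICU stay, a shorter stay lowers the count and can mask or reverse a benefit

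*SAP*

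**What the plan says.** Section 2 of the SAP, under Secondary Hypothesis, lists among the outcomes that MQS should predict "ICU coma- and delirium-free days, ICU ventilator-free days, ICU vasopressor-free days, ICU neuromuscular blocking agent free days". The same sentence opens with "We also hypothesize that the MQS predicts ICU length of stay, hospital length of stay", so the plan itself expects time in the ICU to move with the exposure.

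Under Secondary analyses the model is fixed: "Negative binomial regression will be used to analyze the association between mobilization and the secondary outcomes coma- and delirium-free days, NMBA-free days, ventilator-free days". No offset, time at risk or upper bound is given. Length of stay has its own model: "Zero truncated negative binomial regression will be used to analyze the association between mobilization dose and the secondary outcomes ICU and hospital length of stay". It is not among the predefined confounders, which are APACHE2, PSS morbidity and sex-adjusted RFCSA.

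For the exposure, by contrast, the plan does use a denominator: "The MQS is calculated daily throughout the SICU stay and will be divided by the number of ICU days". Several exploratory mobilization measures in the same section are also divided by ICU days. The free-day outcomes are not.

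**The concern.** A free-day count is meaningful only relative to the days over which it is taken. If that period is the patient's own ICU stay, the count has two parts: how long the patient stayed, and what share of those days was free. A plain negative binomial model reports the product of the two. An exposure that shortens the stay pushes the product down even when it does nothing to ventilation, delirium or neuromuscular blockade, or improves them. An early death also enters as a short stay, with nothing to mark it as the worst result.

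At stake is the interpretation of three secondary outcomes. The trial could report that more mobilization goes with fewer ventilator-free days when the data show only earlier ICU discharge. It could also miss a real benefit because the two parts cancel.

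**Working it through.** **The plan's own figure.** The SAP gives no power or effect size for the free-day outcomes. Its one figure, under Sample Size and Power ("a sample size of 150 patients provides a power of >0.8" for a correlation of 0.25 at alpha 0.05), concerns the primary outcome. It reproduces: atanh(0.25) × √147 − 1.96 = 0.2554 × 12.124 − 1.96 = 1.137, and Φ(1.137) = 0.872, two-sided. That figure is sound, but it says nothing about the outcomes here.

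**Two patients.** Take one with a 6-day stay and 2 affected days, and one with a 12-day stay and 6 affected days.
- Counted within the ICU: 6 − 2 = 4 against 12 − 6 = 6. The sicker patient scores better.
- As a share of ICU days: 4/6 = 0.67 against 6/12 = 0.50. The order is right.
- Over 28 days, with days after ICU discharge free: 28 − 2 = 26 against 28 − 6 = 22. The order is right.

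**Reading 1: days counted within the ICU stay.** All inputs are assumed, because the SAP gives none: mean stay 9 days at mean MQS (one day plus an overdispersed count of mean 8), 45% of ICU days affected, no deaths, no covariates, N = 150, 200 runs per setting.

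Per SD of MQS, let r be the ratio applied to the days beyond the first, and OR the odds ratio for an affected day. The expected free-day ratio is S × F.
- S = (1 + 8r)/9 is the change in stay: 0.911, 0.822 and 0.733 for r = 0.9, 0.8 and 0.7.
- F = (1 − p₁)/(1 − p₀) is the change in the free share, with p₀ = 0.45. For OR 0.8, the odds are 0.818 × 0.8 = 0.655, so p₁ = 0.396 and F = 0.604/0.55 = 1.099. For OR 0.6, the odds are 0.491, so p₁ = 0.329 and F = 0.671/0.55 = 1.220.

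| r | OR | S × F | Plain model: ratio (significant harm) | With log(ICU days) offset: ratio (significant harm) |
|---|---|---|---|---|
| 1.0 | 1.0 | 1.000 | 1.003 (2.5%) | 1.005 (1%) |
| 1.0 | 0.8 | 1.099 | 1.099 (0%) | 1.098 (0%) |
| 0.9 | 1.0 | 0.911 | 0.915 (26.5%) | 1.003 (2%) |
| 0.9 | 0.8 | 1.001 | 1.017 (2.5%) | 1.111 (0%) |
| 0.9 | 0.6 | 1.111 | 1.139 (0%) | 1.257 (0%) |
| 0.8 | 1.0 | 0.822 | 0.826 (81%) | 1.003 (1.5%) |
| 0.8 | 0.8 | 0.903 | 0.919 (24%) | 1.116 (0%) |
| 0.8 | 0.6 | 1.003 | 1.036 (0.5%) | 1.252 (0%) |
| 0.7 | 0.8 | 0.806 | 0.806 (86.5%) | 1.105 (0%) |
| 0.7 | 0.6 | 0.894 | 0.924 (25.5%) | 1.268 (0%) |

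The simulated plain-model ratios follow S × F to within about 0.03. The sign reverses when S × F is below 1. Otherwise the benefit is diluted: at r = 0.8 and OR 0.6, a 1.25-fold rate of free days is reported as 1.04. Two further simulations at stay ratio 0.8 with an unchanged share of affected days gave 0.82 (77% significant harm) and 0.80 (84%), each with 1.00 under the offset.

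**Reading 2: fixed 28-day window, death = 0.** Assumed: N = 150 and 15% deaths. The outcome is bounded at 28 with a spike at zero.
- Null: negative binomial with default standard errors rejected in 0% of runs and with robust standard errors in 5.5%; a rank test rejected in 5.7%.
- MQS affects days but not mortality: default errors gave 0% to 3% power against 29% to 79% for a rank test. With robust errors, one setting (log-ratio of ventilator days −0.3 per SD) gave 25% against 48%.
- MQS also lowers mortality: robust errors gave 56%, 80% and 88% against 59%, 78% and 90% for the rank test at three effect sizes, and 84% against 90% in a separate run.

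**The case against.** The strongest reply is that the SAP never says over which period free days are counted. The prefix ICU appears in the hypothesis but not in the sentence that names the model. A protocol, not at hand, may fix a window and a rule for death, and leaving that derivation to the protocol is ordinary practice. This stands. A reader might infer that the plan does count a longer stay as more free days, so that the sign will reverse; the text supports that only conditionally. With a fixed window in which days after discharge count as free, this reversal does not arise.

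A second reply is that reversal needs particular inputs. This also stands. There is none if the stay does not depend on MQS, nor at r = 0.9 with OR 0.8 or 0.6, although the benefit is still diluted there. None of the inputs comes from the SAP.

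Third, a reader might conclude that negative binomial regression is unusable under a fixed window. That goes too far. Much of the loss comes from default standard errors, and the SAP names no variance estimator. With robust errors the test holds its level and nearly matches a rank test where mortality also moves. A clear disadvantage remains where mortality is unaffected.

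Fourth, vasopressor-free days are in the list of hypotheses, but the SAP does not assign them to this model, so the point does not extend to them.

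The replies do not dispose of the point. The choice of model is made in this document, and without an offset or a bound it does worse than an available alternative under either reading.

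**Conclusion.** The point holds in conditional form for coma- and delirium-free, NMBA-free and ventilator-free days. Under the within-ICU reading, the stated model mixes length of stay into the outcome while the plan expects MQS to predict that stay. The consequence ranges from dilution of a true benefit to significant apparent harm in roughly 80% of trials when only the stay shortens (stay ratio 0.8 per SD). Under a fixed window with death = 0, the model with default errors is very conservative and weak. Robust errors repair its level and part of its power.

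The magnitudes rest on assumed stay, affected-day share, mortality and effect sizes, without covariates; the direction of the distortion follows from S × F. The primary analysis of adverse discharge disposition and the comparison of MQS with SOMS are untouched. The change is worth making before analysis but does not threaten the trial's main result.

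**What to change.** State in the SAP, or by reference to the protocol, the counting window and the rule for death and ICU discharge for each free-day outcome. Then choose one of two routes.

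1. Use a fixed window, for example 28 days from ICU admission, with death as the worst value, and a proportional-odds model with the same covariates. This credits earlier recovery and places deaths explicitly.
2. Keep the ICU-stay count, add log(ICU days) as an offset or model the proportion of ICU days that were free, and report deaths separately. The proportion model also respects the upper bound, which a negative binomial with offset does not.

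The cost is mainly wording, with some loss. Under the first route, status after ICU discharge must be taken from the record or assumed free; the Data collection section specifies no delirium or coma assessment after the ICU. The effect becomes an odds ratio. Under the second, the effect is a rate or share per ICU day, which gives no credit for a shorter stay and so must be read beside the length-of-stay result.
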